For the analysis of total HF hospitalizations component, occurrence of CV death can be regarded as semi-competing risk (informative censoring) and may introduce a bias in the treatment effect estimate for HF hospitalizations (dilution of effect size if the drug has a positive effect on both components). In order to address this concern and to account for the correlation between the two components, the joint modeling (frailty model) approach ([Cowling et al 2006](#)) will be used for the component analyses. The joint model is specified as follows.

$$\begin{aligned}\lambda_{ij}^H(t) &= Y_{ij}(t)\lambda_0^H \exp(\beta_0 x_{ij})\nu_{ij} \\ \lambda_{ij}^T(t) &= Y_{ij}(t)\lambda_0^T \exp(\gamma_0 x_{ij})\nu_{ij}^\alpha \\ \nu_{ij} &\sim f(\cdot)\end{aligned}$$

where $\lambda_{ij}^H(t)$ is the rate function of the total hospitalizations for HF for subject i in region j and λ_0^H is its constant baseline and $\lambda_{ij}^H(t)$ has a similar format as the model described above for the primary endpoint except for the multiplier ν_{ij} that is a subject-specific random effect factor (frailty); and $\lambda_{ij}^T(t)$ is the hazard function for the component of CV mortality for subject i in region j and λ_0^T is its constant baseline and $\lambda_{ij}^T(t)$ is a frailty proportional hazards model. The parameter α measures the association between $\lambda_{ij}^H(t)$ and $\lambda_{ij}^T(t)$. The frailty distribution $f(\cdot)$ is taken to be the Gamma distribution with shape = θ and scale = $1/\theta$. The parameters in the joint model, including the unknown power for the frailty, will be estimated through maximization of the corresponding likelihood. The model assumes that the correlation between total HF hospitalizations and CV death for each patient is completely explained by x_{ij} and the frailty and the two analysis variables corresponding to the two components are independent given the patient's frailty and x_{ij} .

For the analysis of CV death, it will be analyzed using Cox's proportional hazards model with a fixed treatment group factor and stratified by region. The analysis in the joint frailty model for this component, which is actually subject specific, will be considered as supportive for the analysis for CV death whenever an inference is needed for it.

In all the proposed analyses, it is acknowledged that the study will not be powered to achieve statistically significant results for the CV death.

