The proposed joint frailty model assumes a constant baseline intensity and constant baseline hazard model for the recurrent HF hospitalization and CV death components, respectively. The marginal model for the recurrent hospitalizations for heart failure of this joint frailty model is a negative binomial model.

As a sensitivity analysis, the constant baseline intensity function λ_0^H and constant baseline hazard function λ_0^T will be replaced by piece-wise constant functions (i.e. multiple-step

functions). The number of steps in the step functions will be selected based on the Bayesian Information Criterion (BIC). The partitions of these constant step intervals can be obtained based on the equally-divided percentiles (Liu and Huang 2008).

The joint model will be estimated using SAS PROC NLMIXED. The below SAS code illustrates the program for a piece-wise constant intensity and hazard baseline function with 10 steps:

```
proc nlmixed data=data_joint qpoints=5 corr;
parms / data=inpar;
bounds r01 r02 r03 r04 r05 r06 r07 r08 r09 r10 h01 h02 h03 h04 h05 h06
h07 h08 h09 h10 alpha >=0;

/* g is Gamma distributed with mean 1 and variance 1/alpha*/
p=cdf('NORMAL', nu);
if p > .999999 then p=.999999;
g2=quantile('GAMMA', p, alpha);
g=g2 * 1/alpha;
/* baseline hazard and cum baseline hazard, recurrent events */
base_haz_r=r01*event_r1+r02*event_r2+r03*event_r3+r04* event_r4 +
r05*event_r5+r06*event_r6+r07*event_r7+r08*event_r8
+r09 * event_r9 + r10 * event_r10;
cum_base_haz_r=r01*dur_r1+r02*dur_r2+r03*dur_r3+r04*dur_r4 +
r05*dur_r5+r06*dur_r6+r07*dur_r7+r08*dur_r8+r09*dur_r9 +
r10 * dur_r10;
/* baseline hazard and cumulative baseline hazard for death */
base_haz_d=h01*event_d1+h02*event_d2+h03*event_d3+h04*event_d4 +
h05*event_d5+h06*event_d6+h07*event_d7+h08*event_d8+
h09 * event_d9 + h10 * event_d10;
cum_base_haz_d=h01 * dur_d1 + h02 * dur_d2 + h03 * dur_d3 +
h04 * dur_d4 + h05 * dur_d5 + h06 * dur_d6 + h07 * dur_d7 +
h08* dur_d8 +h09 * dur_d9 + h10 * dur_d10;
mu1= beta1 * trt + log(g);/* for recurrent event */
mu2= alpha1 * trt + gamma * log(g); /* for death event */
loglik1=-exp(mu1) * cum_base_haz_r;
loglik2=-exp(mu2) * cum_base_haz_d;
/*log likelihood for recurrent event */
if status_rec = 1 then loglik=log(base_haz_r) + mu1 ;
/*log likelihood for death */
if status_rec = 2 then loglik=loglik1 +log(base_haz_d)+mu2+loglik2;
/*log likelihood for censoring */
if status_rec = 0 then loglik=loglik1 + loglik2;
model time_stop ~ general(loglik);

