random nu ~ normal(0, 1) subject = sid1a;
ods output ParameterEstimates=jm.est FitStatistics=jm.fit;
run;
```

where `data_joint` is the input dataset, `jm.est` and `jm.fit` for the parameter estimates and model fitted statistics. The dataset `inpar` contains the initial guesses for `r01-r10`, `h01-h10` and the other model parameters. The input dataset `data_joint` should include the values of event indicators `event_r1- event_r10` and `event_d1- event_d10` and durations `dur_r1- dur_r10` and `dur_d1- dur_d10`.

A non-parametric estimate of the primary endpoint event rates (Nelson-Aalen estimates) will be provided. Non-parametric estimates of conditional HF hospitalization rates (Nelson-Aalen estimates), given the patient has not died due to a CV reason, over time (Cook and Lawless 1997) and of unconditional HF hospitalization rates over time allowing for death as terminal event will be provided as well (Ghosh and Lin 2000).

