13.1 Power for the primary endpoint

Sample size is calculated through simulations for the proportional rates model. The control group rate of total hospitalizations for HF and rate of mortality are estimated in two steps in order to get a reasonable estimate for the selected patient population.

First we estimate the rates from the candesartan group of the CHARM-Preserved study ([Yusuf et al 2003](#)) for patients with EF >45%, using a joint model that joins the Poisson regression model and the exponential regression model together through a shared gamma frailty ([Cowling et al 2006](#)). An independent uniform censoring on the events are assumed during the follow-up. With the given frailty between HF hospitalization and CV death, the estimated baseline intensity in the Poisson model = 0.00032 HF hospitalizations/day per patient and the estimated hazard rate in the exponential model = 0.000136 CV deaths/day per patient. The estimated gamma shape parameter (the frailty parameter that is also assumed to be 1/scale) is 0.193. These specified parameter values produce approximately an annualized rate of 0.083 for time to first primary event and an annualized rate of 0.036 for CV mortality.

Second, we adjust these estimated rates up by 8% (and then increasing the corresponding Poisson intensity rate and hazard rate) based on the results from the recent completed HF studies and publications, which are believed to reflect a higher risk patient population than that in the CHARM-Preserved study. This leads an annualized rate of 0.09 for time to first primary event and an annualized rate of 0.04 for CV mortality for a high risk patient population.

The target reduction in RR for the primary endpoint is chosen to be about 22%, which approximately corresponds to a reduction of 30% for HF hospitalization and a reduction of 10% for CV death, given the gamma frailty defined above between these two components. With the CHARM-Preserved data structure for EF \geq 45%, the specified rates will produce an approximately 15% reduction for time-to-first event analysis, see [Table 13-1](#).

The patient enrollment is assumed to be uniform lasting 2 years and 5 months and the minimum follow-up is to be 2 years and 2 months.

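### If the five quadrature points in the SAP's illustrative joint frailty code are used, the component intervals come out about 5% too narrow at the planning gamma shape of 0.193

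*SAP*

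**What the plan says.** SAP 9.3.1.1 assigns the component analysis of total HF hospitalizations to a joint model with a shared frailty, to deal with informative censoring by CV death. The main version has a constant baseline intensity and hazard. A piecewise-constant version, with the number of steps chosen by BIC, is a sensitivity analysis. The frailty "is taken to be the Gamma distribution with shape" θ and scale 1/θ, so its mean is 1 and its variance 1/θ. It enters the death hazard raised to an estimated power.

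On computation the SAP states: "The joint model will be estimated using SAS PROC NLMIXED". It then adds: "The below SAS code illustrates the program for a piece-wise constant intensity and hazard baseline function with 10 steps". That code starts with "proc nlmixed data=data_joint qpoints=5 corr", declares "random nu ~ normal(0, 1) subject = sid1a", and turns the normal effect into a gamma variate through the gamma quantile function. Neither document gives another number of points, a quadrature tolerance or a check of quadrature accuracy.

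The planning value of the shape is in SAP 13.1: "The estimated gamma shape parameter (the frailty parameter that is also assumed to be 1/scale) is 0.193".

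On notation, the shape is θ in the SAP text and alpha in the code. The power on death is α in the text and gamma in the code.

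**The concern.** At shape 0.193 the frailty variance is 1/0.193 = 5.2. Most patients have a frailty near zero and a few have a very large one. Written as a function of a standard normal effect, each patient's integrand is then far from Gaussian, and five Gauss-Hermite points may not integrate it well. If the approximation biases the fitted shape upward, heterogeneity between patients is understated and the treatment-effect standard errors shrink with it.

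HF hospitalization is the component planned to carry the effect (30% reduction, against 10% for CV death, in SAP 13.1). The component results serve to check consistency with the composite and are repeated on the per-protocol set. Intervals that are too narrow would make that component look more precisely estimated than it is.

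**Working it through.** **Inputs from the SAP.** Section 13.1: shape 0.193; 4600 patients; uniform accrual over 2 years 5 months with a minimum follow-up of 2 years 2 months (mean 3.375 years); annualized rates 0.09 (first event) and 0.04 (CV death); RR 0.70 for HF hospitalization and HR 0.90 for CV death. Section 9.3.1.1: the likelihood and 5 points.

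**Assumed, because the documents do not say.** The frailty power on death (0.5, 1 and 1.5 tried), and that the software uses adaptive quadrature when no option is named.

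**Step 1: reproduce the plan's own figures.** With intensities calibrated to 0.09 and 0.04 per year, the simulation gives 1812 events (SAP 1847), LWYY rate ratio 0.779 (SAP 0.778) and power 0.938 (SAP 0.95). Multiplying the stated intensities by 1.08 gives only 1636 events, so the calibrated version was used.

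**Step 2: fit the SAP likelihood two ways on the same data.** Patient i contributes the integral over ν of

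[λ_H g exp(βx)]^n · [λ_T g^α exp(γx)]^δ · exp{−T[λ_H g exp(βx) + λ_T g^α exp(γx)]} · φ(ν),

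where g is the gamma(θ) quantile of Φ(ν) divided by θ, n is the number of HF hospitalizations, δ indicates CV death and T is follow-up time. The integral was computed on a dense grid (essentially exact) and with 5 adaptive points. Standard errors (SEs) come from the Hessian of each log-likelihood. With r = SE(5 points)/SE(exact), the coverage of a nominal 95% interval is 2Φ(1.96r) − 1.

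| Shape | Power on death | Data sets | HF hosp. r, mean (range) | CV death r, mean | HF hosp. coverage at mean r |
|---|---|---|---|---|---|
| 0.193 | 0.5* | 6 | 0.961 (0.954–0.968) | 0.999 | 94.0% |
| 0.193 | 1.0 | 25 | 0.952 (0.937–0.968) | 0.951 | 93.8% |
| 0.193 | 1.5* | 6 | 0.922 (0.911–0.933) | 0.905 | 92.9% |
| 0.1 | 1.0 | 5 | 0.858 (0.848–0.869) | 0.859 | 90.7% |
| 0.3 | 1.0 | 6 | 0.986 (0.983–0.989) | 0.985 | 94.7% |
| 0.5 | 1.0 | 6 | 0.998 (0.997–0.999) | 0.996 | 95.0% |
| 1.0 | 1.0 | 5 | 1.000 | 1.000 | 95.0% |

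*RR 0.75 instead of 0.70.

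The lowest HF-hospitalization ratio at shape 0.193 in the table, 0.911, gives 2Φ(1.786) − 1 = 92.6%. With no treatment effect (shape 0.193, power 1, 8 data sets) the mean ratio is 0.949. A separate set of eight simulated trials with the planning parameters gave 0.91 to 0.96.

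**Step 3: is this false precision?** At shape 0.193 and power 1, the 5-point estimates vary between data sets as much as the exact ones (SD ratio 0.987) and shift by 0.002 on average on the log scale. So the reported SE falls while the real variability does not. The mean fitted shape is 0.225 against 0.197 exact, 14% too high. The implied frailty variance is therefore 0.197/0.225 = 0.88 of what it should be.

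**Step 4: the 10-step piecewise version.** In six data sets the HF-hospitalization ratio was 0.943 to 0.967 (for example 0.0906/0.0961 = 0.943), about the same as with a constant baseline.

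**Step 5: more points.** With 9 points the mean ratio is 0.999 (0.997–1.000, 25 data sets) and the fitted shape 0.198. In one data set 15 and 31 points both gave 0.0955, equal to the exact SE. Runs with 20 points also matched.

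**Step 6: log-likelihood.** At shape 0.193 the 5-point log-likelihood was about 13 to 20 units too low.

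**The case against.** Several points against this stand and limit it.

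- **The code is an illustration.** It shows the piecewise sensitivity fit. Its use for the constant-baseline fit is an inference: no other value is given, and the shortfall is about the same there, but the SAP does not prescribe 5 points for the main component analysis.
- **The shape is a planning value.** It comes from the candesartan arm of another trial. A reader might infer that this trial's intervals will be 4% to 9% too narrow. The documents do not support that as a prediction, because the fitted shape is unknown and the shortfall runs from about 14% at 0.1 to nothing at 1.0. The upper end of 4% to 9% also needs a power on death of about 1.5 in the runs tabulated above.
- **The analyses are supportive.** A reader might infer that the primary result is at risk. It is not: the LWYY test uses no quadrature, CV death is analysed by a stratified Cox model, and the components receive no alpha in the testing procedure. SAP 9.3.1.2(f) also plans an LWYY analysis of HF hospitalizations alone, and 9.3.1.1 adds non-parametric estimates. An over-narrow joint-model interval would therefore not stand alone. Protocol 9.4.2.1 does still foresee an inference on HF hospitalizations once the composite is positive, so the interval is not without weight.
- **The BIC choice.** It is tempting to say that the log-likelihood error corrupts the choice of steps. BIC compares fits, and much of the error may cancel. In three runs with 1, 2 and 4 steps the error varied between step counts by 1.3, 2.5 and 5.5 units. The chosen number changed only in one run, built with a hospitalization rate that halved after six months. An effect is possible but not shown for this trial.
- **Adaptive quadrature is an assumption about the software.** Non-adaptive 5-point integration does no better: mean ratio 0.942 (0.903–0.973), with less stable estimates.

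**Conclusion.** The point holds conditionally. If five points are used for the joint-model component analyses and the fitted shape is near 0.193, the HF-hospitalization SE is about 5% too small at power 1, and about 4% to 9% too small over powers 0.5 to 1.5. A nominal 95% interval then covers about 92.5% to 94%. For the supportive CV-death estimate from the same model the shortfall is also about 5% at power 1, but ranges from almost none at power 0.5 to about 9.5% at power 1.5. The error runs towards overstated precision.

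This rests on the planning shape, the assumed powers and the code setting being carried into the actual fits. It concerns the joint-model component analyses and their per-protocol repeat, and no confirmatory test.

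**What to change.** State the number of quadrature points in SAP 9.3.1.1 for both the constant-baseline and the piecewise joint models, and raise it above 5. Nine nearly suffices at shape 0.193; 15 to 20 leaves margin if the fitted shape is smaller. Because the shape is not known in advance, also require that estimates, SEs and log-likelihood are stable when the number of points is increased further, and make the BIC comparison only on fits that pass this check. The model and the estimand do not change. The cost is one option in the code and longer run time.

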9.3.1.2 Supportive analyses for primary efficacy

The supportive analyses for the primary analysis results will be performed in two ways:

- 1) Evaluating the impact of the informative censoring of CV death on the estimate of the relative rate reduction through performing additional analyses including:
 - a. Checking of existence of any non-negligible imbalance in CV mortality between treatment groups through analysis for CV mortality alone. This analysis will be performed using Cox's proportional hazards model for time-to-CV death. If it deems necessary, pooling appropriate patient (sub-) population from PARADIGM-HF (CLCZ696B2314) and this study will be performed using the same Cox model to further assess any adverse signal on CV mortality between treatments;
- 2) Providing a series of sensitivity analyses to investigate the robustness and consistency of the primary efficacy results:
 - b. Performing the primary analysis (the LWYY model) and the component analyses (the joint frailty model) on the PPS;
 - c. Analysis using the WLW method (Wei et al 1989, Li and Lagakos 1997) on time to first (the conventional time-to-first event analysis) and time to 2nd, 3rd, 4th, 5th, and 6th composite events; an average effect (stratified by event number) will be provided for each of those analyses. This analysis will partially evaluate the robustness of the overall estimate of effect size against the impact from an (expected) small subgroup of patients with higher number of hospitalizations for HF. If the patient's first event is a CV death, then his 2nd, 3rd, ..., Kth event will be counted as CV death as well. This analysis avoids informative censoring by counting CV death repeatedly as event. It is acknowledged that some of the analyses, time-to-1st event, for example, may not be powered;
 - d. Analysis using a negative binomial regression model (McCullagh and Nelder 1989) on total number of primary composite endpoints with an offset of logarithm of time from randomization to censoring or death. The common rate ratio of composite events will be provided;
 - e. Analysis using a multi-state model (Castaneda and Gerritse 2010) to assess the hazard ratios of transition intensities between different states defined by hospitalization status and CV death;

- f. Performing the analysis for recurrent heart failure hospitalizations using the same LWYY model used for the primary endpoint with the conditional rate ratio. A weighted-pooled effect size and its 95% CI, using the results from this analysis and the Cox regression analysis for CV death outlined in 1), will also be provided. The estimated optimal weights will be obtained through the estimated covariance matrix of the two estimates of the component effect sizes.
- 3) Evaluating treatment effect on time to first primary composite event (cardiovascular death or hospitalizations for heart failure). The time to first primary composite event will be analyzed using Cox proportional hazards model with treatment as fixed factor and stratified by region. Additionally, a log-rank test will be performed.
- 4) Some additional supportive analyses may be performed.

Analysis using the multi-state models

The multi-state model utilized in this study is described in [Figure 9-1](#). The transition intensities are defined as follows.

$h_{ij}^{EH}(t) = Y_{ij}^H(t)\rho_{0j}^{EH}(t)\exp(\alpha x_{ij})$ for being hospitalized for heart failure (*H*) at time *t* from the state of event free (*E*);

[figure not shown]
$h_{ij}^{ED}(t) = Y_{ij}^D(t)\rho_{0j}^{ED}(t)\exp(\beta x_{ij})$ for experiencing CV death (*D*) at time *t* from the state of event free (*E*);

$h_{ij}^{HH}(t) = Y_{ij}^H(t)\rho_{0j}^{HH}(t)\exp(\gamma x_{ij})$ for being re-hospitalized for heart failure (*H*) at time *t* after being previously hospitalized for heart failure (*H*);

$h_{ij}^{HD}(t) = Y_{ij}^D(t)\rho_{0j}^{HD}(t)\exp(\vartheta x_{ij})$ for experiencing CV death (*D*) at time *t* after being previously hospitalized for heart failure (*H*);

where *i* and *j* stand for subject *i* in rejoin *j*, $Y_{ij}(t)$ s are the at-risk (to *D* or to *H*) indicators, and x_{ij} is the treatment group indicator defined above taking value 0 or 1.

Figure 9-1 Scheme of the multi-state model

In this model, we have assumed that the transition intensities for recurrent hospitalization for HF are proportional; and that all transition intensities for recurrent hospitalization for HF to CV death are proportional. We have four transition intensities to be modeled.

The data structure for analysis has a form below:

patid	time_start	time_stop	status	from	to	transition	time	treatment	region
1	0.00	8.70	0	E	H1	E -> H	8.70	1	1
1	0.00	8.70	0	E	D	E -> D	8.70	1	1
2	0.00	6.30	0	E	H1	E -> H	6.30	0	1
2	0.00	6.30	1	E	D	E -> D	6.30	0	1
3	0.00	2.25	1	E	H1	E -> H	2.25	1	2
3	0.00	2.25	0	E	D	E -> D	2.25	1	2
3	2.25	6.75	1	H1	H2	H -> H	4.50	1	2
3	2.25	6.75	0	H1	D	H -> D	4.50	1	2
3	6.75	11.36	0	H2	H3	H -> H	4.61	1	2
3	6.75	11.36	0	H2	D	H -> D	4.61	1	2
4	0.00	2.25	1	E	H1	E -> H	2.25	0	2
4	0.00	2.25	0	E	D	E -> D	2.25	0	2
4	2.25	6.75	1	H1	H2	H -> H	4.50	0	2
4	2.25	6.75	0	H1	D	H -> D	4.50	0	2
4	6.75	11.36	0	H2	H3	H -> H	4.61	0	2
4	6.75	11.36	1	H2	D	H -> D	4.61	0	2

where `status` is 0 for censored and 1 for event.

The below R code can be used for the analysis.

```
> library(survival)
> fit1 <- coxph(Surv(start, stop, status) ~ factor(transition_trt) +
cluster(patid) + strata(transition_region) , data=recurent_data)
```

or

```
> fit1 <- coxph(Surv(start, stop, status) ~ factor(trt) + cluster(patid) +
strata(region) , data=recurent_data, subset=(transition=='E2H')) where
transition_region is the derived from combination of transition and region,
transition_trt is the derived from combination of transition and trt.
```

On-treatment LWYY analysis

On-treatment analysis is referring to the supportive analysis for the primary endpoint based on the FAS and with events censored after premature discontinuation of study drug. Specifically, the patient-specific follow-up period will be truncated at the date of last study drug intake + 29 days. Accordingly, the date of last study drug intake + 29 days will be used as censoring if smaller than the censoring date defined in Section 9.2.

Various death components used in composite endpoint

The LWYY analysis will be repeated replacing the CV death component in the primary endpoint with the following (less disease-specific) components as supportive analyses:

- Death due to CV or unknown cause;

- All-cause death

Time-dependent systolic blood pressure (SBP) covariate adjusted analyses

The analyses will be performed as supportive analyses to explore whether the treatment effect is driven by SBP changes:

- LWYY analysis for the primary composite endpoint of CV death and total heart failure hospitalizations;
- Cox proportional hazards model mentioned in (3) for the first primary composite endpoint.

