9.3.1.1 Analysis for primary endpoint

The primary efficacy endpoint of the study consists of the times to recurrent hospitalization due to heart failure and death time due to CV reasons during the patient's follow-up. The comparisons between two treatment groups will be made using statistical procedures which deal with such multiple event time observations. The semi-parametric proportional rates model (abbreviated as LWYY model) (Lin et al 2000) will be utilized for quantifying the treatment difference.

Specifically, let $\lambda_{ij}(t, x_{ij})$ be the individual rate of primary composite events for subject i in region j , given that the patient has not died from a CV reason at time t . It is dependent on the time from randomization (t) and treatment group (x_{ij}). Let $x_{ij} = 1$ if the subject is in the LCZ696 group and $x_{ij} = 0$ if the subject is in the valsartan group.

Under the proportional rates model, the individual rate function for the composite endpoint of CV death and total HF hospitalizations is assumed to be, $\lambda_{ij}(t, x_{ij}) = Y_{ij}(t)\lambda_{0j}(t)\exp(\beta_0 x_{ij})$, where $Y_{ij}(t) = 1$ if subject i in region j is at risk for HF hospitalization or CV death at time t and $Y_{ij}(t) = 0$ if subject i in region j is censored or died from a CV reason at time t – and $\lambda_{0j}(t)$ is the baseline rate function for the event in region j . ($Y_{ij}(t) = I(\min(T_{ij}, C_{ij}) \geq t)$, where T_{ij} and C_{ij} are CV death time and censoring time for subject i in region j . $I(\cdot)$ is an indication function.)

The primary hypothesis to be tested is, $H_{10}: \beta_0 \geq 0$ versus $H_{1a}: \beta_0 < 0$, where $\exp(\beta_0)$ is the relative risk or rate ratio (RR) of total hospitalizations for HF and CV death in the LCZ696 group relative to the valsartan group given the patient has not died from a CV reason at time t , which is assumed to be constant over time and across regions.

The primary hypothesis could be equivalently written as:

H_{10} : Rate ratio LCZ696/valsartan ≥ 1 versus H_{1a} : Rate ratio LCZ696/valsartan < 1 ,

A rate ratio < 1 indicates an effect in favor of LCZ696.

Note that $\exp(\beta_0)$ can also be considered as a ratio of two mean cumulative frequencies of a subject having hospitalizations for HF and CV death when the rate ratio is constant over time and CV mortality is balanced between treatment groups.

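### The first illustrative multi-state R call in SAP 9.3.1.2 has three aliased coefficients and, with 0/1 arm coding, prints hazard ratios in mixed directions

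*SAP*

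**What the plan says.** SAP 9.3.1.2 lists a multi-state analysis as item 2(e) among the sensitivity analyses of the primary result. It models event-free to HF hospitalization (E→H), event-free to CV death (E→D), rehospitalization (H→H) and CV death after hospitalization (H→D): "We have four transition intensities to be modeled". Each intensity carries one treatment coefficient on x, which "is the treatment group indicator defined above taking value 0 or 1". SAP 9.3.1.1 gives x the value 1 "if the subject is in the LCZ696 group and" the value 0 for valsartan, and says that a ratio below 1 favors LCZ696.

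R code then follows as something the analyst may use. The first call has the formula "Surv(start, stop, status) ~ factor(transition_trt") and continues "cluster(patid) + strata(transition_region) , data=recurent_data". Of its two constructed variables, "transition_region is the derived from combination of transition and region" and "transition_trt is the derived from combination of transition and trt". A second call, offered as an alternative, fits treatment within one transition (E→H is the example), stratified by region. The SAP gives no reference level, no contrast and no instruction for reading the coefficients of the first call.

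**The concern.** The formulas ask for four coefficients, all in the direction LCZ696 over valsartan. The first call supplies seven columns, inside strata that already hold transition fixed. Some of those columns must be redundant, and the software's default ordering decides which arm each surviving coefficient describes. If the two arms survive in a mixture, one output table holds hazard ratios in opposite directions.

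At stake is the readability of a prespecified robustness analysis. The transitions into HF hospitalization carry most of the expected effect (SAP 13.1 plans on a 30% reduction in HF hospitalization and 10% in CV death). Values copied from the output without attention to the labels would show a benefit there as a ratio above 1, beside a correctly oriented E→D.

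**Working it through.** **Inputs.** Four transitions and 0/1 arm coding with LCZ696 = 1 (SAP 9.3.1.2 and 9.3.1.1); covariate = transition combined with arm; strata = transition combined with region.

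**Column count.** 4 transitions × 2 arms = 8 levels, hence 8 − 1 = 7 dummy columns. Default sorting makes E→D, arm 0 the reference.

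**Estimable columns.** Transition is constant within each stratum, so the partial likelihood depends only on the difference between the two arms' linear predictors for that transition.

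- E→D: the arm 0 dummy is the reference, so the arm 1 coefficient is the log hazard ratio LCZ696/valsartan. One estimable column.
- E→H, H→H and H→D: both arm dummies are present and sum to 1 within the stratum. Only b1 − b0 is identified, which gives one estimable column for each transition.

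The rank is 1 + 3 = 4, matching the four effects that the SAP says are to be modeled, and 7 − 4 = 3 columns are aliased. Centering the design matrix of the SAP's own 16 example rows within strata gives the same result: 8 levels, 7 columns, rank 4.

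**Direction.** R keeps the earlier column of each redundant pair (arm 0, valsartan) and sets the later one (arm 1) to NA. With b1 absent, −b0 is the log hazard ratio LCZ696/valsartan, so the printed exp(b0) = 1/HR.

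**Numerical check.** Both calls were run in R 4.3.3 (survival 3.8.3) on simulated data: 4600 patients, 1:1, five regions. The true hazard ratios were assumed to be 0.70, 0.90, 0.75 and 0.60 for E→H, E→D, H→H and H→D, and the baseline rates were also assumed.

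| Transition | First call, row printed | exp(coef) | LCZ696 row | Second call, LCZ696/valsartan |
|---|---|---|---|---|
| E→D | arm 1 | 0.868 | 0.868 | 0.868 |
| E→H | arm 0 | 1.386 | NA | 0.722 |
| H→H | arm 0 | 1.457 | NA | 0.686 |
| H→D | arm 0 | 1.668 | NA | 0.599 |

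The three values above 1 are the reciprocals of the last column: 1/0.722, 1/0.686 and 1/0.599, up to rounding in the third decimal. R gave no warning. A separate simulated data set with frailty gave coefficients of +0.258, +0.313 and +0.068 for E→H, H→H and H→D from the first call, against −0.258, −0.313 and −0.068 from the second; E→D was −0.036 in both.

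**Same fit.** A four-column version (numeric treatment by transition, same strata) gave 0.868, 0.722, 0.686 and 0.599, with no NA. Its log partial likelihood, −20434.83, equals that of the first call.

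**Dependence on labelling.** Putting arm before transition, using arrow labels, or using R's `interaction()` gave the same three inversions. With arm names as labels, LCZ696 sorts before valsartan and only E→D inverts (1.152 = 1/0.868); three columns are still aliased. With all control rows pooled into one level there are 5 levels, 4 columns, no NA and no inversion.

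**The case against.** The strongest reply is that the SAP's formulas, not its code, define the estimand. They are complete and correctly oriented, and the code is a sketch. Its variable names do not match the example data layout (`start` against `time_start`, `trt` against `treatment`, E2H against an arrow label), and the programmer has to build both combined variables. The number of inverted transitions therefore depends on a coding that the SAP does not fully specify. This stands, and it is why the count of three has to be stated conditionally. Even so, 0/1 is the SAP's own coding, and eight levels is the natural reading of a combination of transition and arm.

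It also stands that nothing is mis-estimated. R drops aliased columns automatically, the likelihood is unchanged, and the intended ratios can be recovered exactly. The NA rows and the arm 0 suffix are visible to a careful reader, and the second call would expose the difference at once.

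A reader might infer that the multi-state analysis would report harm where there is benefit. The documents do not support that: it would require someone to ignore three NA rows and present a coefficient labelled as the valsartan level as the LCZ696 effect. What the objection does not remove is that the SAP offers as alternatives two calls whose printed ratios run in opposite directions for three transitions under its own coding, with no note on how to read them.

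**Conclusion.** The point holds as a low-severity parameterization and labelling error in illustrative code. Three of the seven coefficients are aliased whenever the combined variable has eight levels. Under 0/1 coding and default ordering, E→H, H→H and H→D print as valsartan/LCZ696 and E→D as LCZ696/valsartan; other labellings invert one transition or none.

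Two stronger readings should be resisted. One is that three inversions are inevitable: they rest on the coding and ordering just stated. The other is that the trial's conclusions are at risk: the analysis is supportive, carries no alpha, and shares no code with the primary LWYY model, the Cox model for CV death or the joint frailty model. The simulated hazard ratios only illustrate the reciprocal relation; they are not estimates or predictions for this trial.

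**What to change.** Delete the first call and run the per-transition call for all four transitions. Alternatively, replace the covariate with `trt:factor(transition)`, with `trt` numeric (1 = LCZ696), keeping `strata(transition_region)` and `cluster(patid)`. In either case, add a sentence stating that every transition hazard ratio is LCZ696 over valsartan. The cost is one line of code and one sentence, with no change to the model, the data or any other analysis.
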